8.1.2 DEFINITION OF SERIOUS ADVERSE EVENTS (SAE)

An AE will be classified as an SAE if:

- It results in death (i.e., the AE actually causes or leads to death).
- It is life threatening (i.e., the AE, in the view of the investigator, places the subject at immediate risk of death. It does not include an AE that, had it occurred in a more severe form, might have caused death).
- It requires or prolongs inpatient hospitalization.
- It results in persistent or significant disability/incapacity (i.e., the AE results in substantial disruption of the subject's ability to conduct normal life functions).
- It is considered a significant medical event by the investigator based on medical judgment (e.g., may jeopardize the subject or may require medical/surgical intervention to prevent one of the outcomes listed above).

8.2 CLASSIFICATION OF AN ADVERSE EVENT

8.2.1 SEVERITY OF EVENT

The severity of each adverse event must be recorded as 1 of the choices on the following scale:

Mild	No limitation of usual activities
Moderate	Some limitation of usual activities
Severe	Inability to carry out usual activities

An AE that is assessed as severe should not be confused with a SAE.

8.2.2 RELATIONSHIP TO EITHER STRATEGY OF CARE

Each reported AE will be described by its duration (i.e., start and end dates), regulatory seriousness criteria if applicable, and suspected relationship to study drug in accordance with definitions set forth at each IRB. In general, these relationships are categorized as likely, possible, unlikely and not related. Experience teaches that gray zone instances

will arise, and the site coordinators and PIs will be trained to adjudicate possible SAEs in a systematic fashion. To ensure consistency of SAE causality assessments, investigators will apply the following general guideline:

Yes - There is a plausible temporal relationship between the onset of the AE and administration of the study drug and the AE cannot be readily explained by the subject's clinical state, inter-current illness, or concomitant therapies; and/or the AE follows a known pattern of response to study drug or the AE abates or resolves upon discontinuation of study drug;

No - Evidence exists that the AE has an etiology other than the study drug (e.g., preexisting medical condition, underlying disease, inter-current illness, or concomitant medication); and/or the AE has no plausible temporal relationship to the study drug.

Adjudication of each AE will proceed as follows: First, the coordinator will consult the site PI to review the chart. Next, the PI will contact members of the clinical care team to clarify uncertainty related to inadequate documentation. Third, if the PI is unable to decide for certain if an AE or SAE occurred, he or she will have the option of sending a personal health identifier-stripped, written narrative of the event to the other site PIs who will vote up or down as to whether the event constituted an AE or SAE.

8.2.3 EXPECTEDNESS

The following signs, symptoms, observations and events are frequently observed in association with acute heart failure: dyspnea, orthopnea, paroxysmal nocturnal dyspnea, chest pain, fever, hypoxemia, rapid pulse, rapid respiratory rate, dizziness, syncope, altered mental status, confusion, anxiety, generalized weakness, anorexia, nausea, abdominal pain, back pain, early satiety, vomiting, pneumonia, acute renal failure, skin infection, cancer, surgery not related to treatment of pulmonary embolism, electrocardiography abnormalities (atrial arrhythmias, ventricular dysrhythmias, right bundle branch block, and ST and T wave changes), elevated troponin level, elevated BNP or NT ProBNP level, high white blood cell count, pulmonary infiltrate, pleural effusion, cardiomegaly, electrolyte imbalances, need for oxygen therapy, need for vasopressor support, need for blood product transfusion, need for mechanical ventilation (invasive or non-invasive), need for physical or occupational therapy, need for analgesia, need for skilled nursing facility upon discharge, need for early follow up with physician, escalation of heart failure therapy, need for cardiac catheterization or PA line placement, need for sleep study.

8.3 TIME PERIOD AND FREQUENCY FOR EVENT ASSESSMENT AND FOLLOW-UP

All AEs and SAEs will be followed through resolution, stabilization, or until the subject is lost-to-follow-up.

The onset and end dates, duration, action taken regarding study drug, treatment administered, and outcome for each adverse event must be recorded on the CRF for randomized patients. The relationship of each adverse event to study drug treatment and study procedures, and the severity and seriousness of each adverse event, as judged by the Investigator, must be recorded as described below.

8.4 REPORTING PROCEDURES

8.4.1 ADVERSE EVENT REPORTING

The study period during which AEs must be reported begins after informed consent is obtained and initiation of study treatment and for 5 days after ending study treatment. Patients will be followed for 30 days for ED visits, re-hospitalization, and mortality. Subject's hospital discharge summaries will be examined at hospital discharge and all non-exempt AEs will be investigated by examining necessary medical records.

8.4.2 SERIOUS ADVERSE EVENT REPORTING

All SAE's will be reviewed within 48 hours and all AE's within 7 days of discovery by the Study team

15 Calendar Day Written Report

The Investigator will also be required to notify the IRBs and all participating investigators, in a written Safety Report, of any serious, unexpected AE that is considered reasonably or possibly related to the strategy-of-care arm

72 hour reporting

For the discovery of an unexpected serious adverse event thought to be related to study, the IRB will be informed within 72 hours.

8.5 STUDY HALTING RULES

As a small pilot study, there are no formal stopping rules.

8.6 SAFETY OVERSIGHT

The PIs will be monitoring the study continuously throughout the study.

A monitoring check will be performed at 50% enrollment (35 patients) and the following will be reviewed:

1. Mortality
2. Re-hospitalizations
3. ICU utilization
4. NIV and intubation
5. Kidney function closest to discharge

9 CLINICAL MONITORING

Sites will be remotely monitored. Should the need arise for further investigation, an independent monitor will be appointed to visit sites. Each site has extensive clinical trial experience and the expectation for this need is low. Nevertheless, the PI will visit each site at least once per year for meeting with study staff and random surveillance.

10 STATISTICAL CONSIDERATIONS

10.1 STATISTICAL AND ANALYTICAL PLANS

Previous work demonstrates the value of B-lines to improve both diagnosis and prognosis in AHF.

10.2 STATISTICAL HYPOTHESES

- *Hypothesis 1a: Nitrate intense treated patients will have less congestion, defined by LUS B-lines, than diuretic intense patients at 6 hours after start of treatment.*
- *Hypothesis 1b: Nitrate intense treated patients will have greater dyspnea relief than diuretic intense patients at 6 hours after start of treatment.*
- *Hypothesis 2: Each site (n=3) will enroll ~2 patient per month for 12 months.*

10.3 ANALYSIS DATASETS

The Full Analysis Set (FAS) will include all randomized patients. In accordance with the intent-to-treat principle, patients will be analyzed by the group to which they were randomized. Misrandomized patients (patients randomized in error

who did not receive any study intervention) will be excluded. Analyses in the FAS will constitute the main efficacy results for the primary and secondary study efficacy endpoints.

The Per Protocol Set (PPS) will be a subset of the FAS and will exclude patients with major protocol violations. The major protocol violations that will result in exclusion from the PPS will be identified prior to unblinding the treatment assignments for final analysis. Patients will be analyzed in the treatment group to which they were randomized. Results of analyses in this analysis population will support the primary efficacy analyses in the FAS.

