6.1 STUDY AGENT(S) AND CONTROL DESCRIPTION

This study will test a nitrate intense vs. diuretic intense early AHF strategy. No investigational therapies will be used. No drugs or therapies that are not approved by the FDA will be allowed.

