6.1.2 DURATION OF THERAPY

Both arms will continue until 6 hours after randomization. 6 hours was chosen to avoid confounding by patients with overly long ED LOS. At minimum, patients should receive at least one round of treatment. The protocol continues even if patients reach the floor. However, if in the opinion of the investigator, the protocol should not be continued once on the hospital floor, this is allowed and should be marked on the case report.

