10.4.3 ANALYSIS OF THE PRIMARY EFFICACY ENDPOINT(S)

The total number of B-lines at the conclusion of ED AHF management

We will examine the distribution of B-lines measurements for the groups with and without events separately. Both absolute number and relative change will be evaluated. Receiver Operating Characteristic (ROC) curves will be plotted together with area under the curve (AUC) calculated to understand the prediction performance of the B-line measurements. Sensitivity, specificity, positive and negative predictive values will be computed at a number of thresholds of B-line measurements to understand the trade-off between false positive and false negative. Confidence intervals of statistical measures will be constructed using the bootstrap method.⁹¹ Although 15 B-lines have been previously identified as a valid threshold, an alternative number may be more useful in the ED setting.

Potential covariates will also be considered in a logistic regression setting to improve precision, which includes baseline co-morbidities, baseline medications (in particular guideline recommended therapies) in-hospital medications, baseline renal function, serum sodium, natriuretic peptide levels, troponin levels, renal function, baseline blood pressure, and discharge medications. Variables such as physical exam, other vital signs, and hemoconcentration may also be included. These covariates are known markers of risk and are standard of care assessments for the vast majority of AHF admissions. Covariates with univariately significant association with the outcome will be included together with the treatment indicator in a logistic regression model. Due to limited sample size, we will limit the number of covariates (including treatment indicator) such that there is 10 events per covariate.

ANALYSIS OF THE SECONDARY ENDPOINTS

1. Dyspnea will also be assessed using a 5-point and 7-point Likert scale.

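### Section 10.4.3 lets variables that arise after randomization into the logistic model that carries the treatment indicator, which can distort the arm effect and does not improve its precision

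*Combined protocol and SAP*

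**What the plan says.** Section 10.3 defines the Full Analysis Set and its grouping: "In accordance with the intent-to-treat principle, patients will be analyzed by the group to which they were randomized". It adds: "Analyses in the FAS will constitute the main efficacy results for the primary and secondary study efficacy endpoints".

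Section 10.4.3 covers the primary endpoint, the total B-line count. It proposes covariates in a logistic regression with the aim of better precision. After baseline co-morbidities and medications, the list runs: "in-hospital medications, baseline renal function, serum sodium, natriuretic peptide levels, troponin levels, renal function, baseline blood pressure, and discharge medications". Renal function therefore appears twice, once with the word baseline and once without. The section continues: "Variables such as physical exam, other vital signs, and hemoconcentration may also be included". Selection is by univariate testing: "Covariates with univariately significant association with the outcome will be included together with the treatment indicator in a logistic regression model". Model size is capped: "we will limit the number of covariates (including treatment indicator) such that there is 10 events per covariate". No sentence limits the candidates to values recorded before randomization.

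Three other places bear on this:

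- Section 6.1: "This study will test a nitrate intense vs. diuretic intense early AHF strategy". Section 6.1.2 adds: "The protocol continues even if patients reach the floor".
- The secondary-endpoint text under 10.4.3 compares the proportion with B-lines ≤ 15 by Chi-square or Fisher's exact test, without covariates.
- Section 10.4.4 proposes a proportional odds model comparing the arms on days alive and out of hospital (DAOOH), and there names baseline covariates only.

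**The concern.** A covariate improves the precision of a randomized comparison without changing its meaning only if assignment cannot have affected it. Several candidates in 10.4.3 fail that test on the plan's own terms.

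- **In-hospital medications.** The arms differ in the intensity of nitrate and diuretic given, and the assigned strategy may continue on the ward. Exposure to these drugs in hospital is largely what was randomized.
- **Discharge medications.** For admitted patients these are settled after the primary B-line reading, which the Protocol Summary places no later than 6 hours after enrollment.
- **Hemoconcentration and later renal function.** Both can result from diuresis. Section 2.3.1 says pre-discharge eGFR will be examined to learn whether the strategy is associated with worsening renal function, so the plan itself treats it as an outcome.
- **Physical exam.** Change in exam findings is an exploratory endpoint in 4.2.2, yet exam may enter this model with no baseline label.

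The arm coefficient would then estimate whatever is left of the strategy's effect after holding part of its mechanism fixed, and it can be biased. Univariate screening worsens this, because a variable that carries the treatment effect tends to be associated with the outcome. Naming these covariates in advance would not cure the problem. Section 3 says the pilot is to inform a larger, definitive trial, and an arm estimate adjusted for treatment delivered would misinform it.

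**Working it through.** **1. The plan's own figure.** Section 10.5 gives 35 per arm, effect size 0.7, two-sided 0.05 and 82% power. The exact two-sample t-test gives 82.3% and the normal approximation 83.4%, so the figure reproduces. The target of 7 B-lines implies SD = 7/0.7 = 10. This 82% belongs to an unadjusted comparison of the count, not to a logistic model.

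**2. What the cap admits.** With treatment counted, k terms need 10k events, so one covariate beside treatment needs 20 events and two need 30. Out of 70 patients:

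| Event proportion | Events | Terms allowed | Covariates beside treatment |
|---|---|---|---|
| 25% | 17.5 | 1 | 0 |
| 30% | 21 | 2 | 1 |
| 40% | 28 | 2 | 1 |
| 50% | 35 | 3 | 2 |

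The 25% row uses the Protocol Summary's background figure for death or re-hospitalization within 30 days. If that is the outcome, no covariate fits. If the outcome is a B-line threshold met by about half the patients, up to two can enter.

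**3. Unadjusted logistic benchmark.** Assume means of 25 and 18 lines, SD 10, and a split at 21.5 (near the median; an assumption).

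- Proportions at or below the split: Φ(−0.35) = 0.363 and Φ(0.35) = 0.637.
- Log odds ratio: 2 × ln(0.637/0.363) = 1.12. The simulated median estimate is about 1.18.
- SE: √[2/(35 × 0.363 × 0.637)] = 0.497.
- Power: Φ(1.12/0.497 − 1.96), about 0.62. Simulation gives about 60%.

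**4. Adding one post-randomization covariate.** Let a dose variable correlate r with arm and carry a share s of the effect. The documents give neither figure; r = 0.5 to 0.7 and s = 0, 0.5 and 1 are assumptions. With two equal arms, r corresponds to a between-arm dose shift of 2r/√(1 − r²) SD, that is 1.15 SD at r = 0.5 and 1.96 SD at r = 0.7. To a first approximation the arm coefficient becomes (1 − s) times its value, and its SE grows by 1/√(1 − r²).

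- s = 0, r = 0.5: SE = 0.497/√0.75 = 0.574, power about Φ(1.12/0.574 − 1.96) = 50%.
- s = 0, r = 0.7: SE = 0.497/√0.51 = 0.696, power about Φ(1.12/0.696 − 1.96) = 36%.

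Simulation of the logistic model agrees with these approximations:

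| Share of effect through dose | Log odds ratio with dose in the model | Power for the arm effect |
|---|---|---|
| No dose term (benchmark) | about 1.18 | about 60% |
| None | no bias from adjustment | about 35–49% (dose forced in) |
| Half | about 0.6 | about 20% (after univariate screening) |
| All | about 0 | 4–5% |

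The loss in the row marked None comes only from collinearity between dose and arm. It is the opposite of the precision gain that 10.4.3 gives as its reason for adjusting.

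**The case against.** The best defence is that this model is supplementary and mostly prognostic. Covariates are to be considered rather than required. The surrounding text speaks of groups with and without events, ROC curves, sensitivity and markers of risk, which fits 30-day outcomes better than a 6-hour B-line count. The logistic outcome is never defined, and at 25% events the cap shuts every covariate out. The Chi-square or Fisher test of B-lines ≤ 15 stays unadjusted. The plan also calls itself a small, exploratory pilot.

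Much of that stands, and it limits how often harm would occur. It does not make the rule sound: the text puts the selected covariates beside the treatment indicator, under the primary endpoint, with no baseline restriction.

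Some details are also uncertain. That in-hospital medications include the randomized drugs is an inference, though a natural one, and 10.4.2 plans to summarize loop diuretic doses by arm. The second mention of renal function may be a drafting repeat. Natriuretic peptide, troponin and electrolytes are scheduled only at screening in 7.3.4, so they are in effect baseline already.

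Three stronger readings are tempting but unsupported.

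- A reader might infer that the plan breaks its intent-to-treat commitment. Section 10.3 governs who is analysed and in which group, and this model can respect both. The fault lies in the covariates.
- A reader might infer that no other model compares the arms. The proportional odds model for DAOOH does, with baseline covariates.
- A reader might measure the loss from the 82% in 10.5. That figure is for the count; the logistic benchmark is about 60%.

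**Conclusion.** The covariate rule in 10.4.3 is wrong as written and should be fixed. It admits consequences of the assigned strategy into the only model with treatment in the primary and secondary endpoint sections, and 10.4.3 states no other between-arm comparison of the B-line count.

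The direction of the loss in the illustration follows from the effect running through the added covariate; other mechanisms could bias the estimate differently. Its size rests on the assumed correlation, mediated share and split point, and it applies only if the outcome yields at least 20 events and such a covariate is selected. The documents do not support saying that the trial will report no difference for this reason: inclusion is optional, and the unadjusted test of B-lines ≤ 15 would be reported alongside.

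**What to change.** In 10.4.3:

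- State that any model containing the treatment indicator uses only covariates recorded before randomization.
- Remove in-hospital medications, discharge medications and hemoconcentration from that model.
- Specify baseline values of renal function, physical exam and vital signs.
- Keep the post-randomization variables for prognostic analyses of 30-day outcomes that make no treatment-effect claim, or report them by arm as a description of care delivered.

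The same edit should define the outcome of the logistic model and name the between-arm comparison of the B-line count, since restricting the covariates would not supply either.

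The cost is a wording change to the analysis plan. It needs no extra patients, data or procedures, and the sample size is unchanged.

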10.4 DESCRIPTION OF STATISTICAL METHODS

10.4.1 GENERAL APPROACH

As a small, exploratory, pilot study, we are uncertain the difference, if any, between the two arms in regards to B-lines after treatment. Unless stated otherwise, two-sided p values < 0.05 will be considered statistically significant, without regard to multiple comparisons. Statistical tables and listings and analyses will be produced using SAS® release 9.1 or later (SAS Institute, Inc, Cary, NC, USA) or other validated statistical software.

10.4.2 BASELINE DESCRIPTIVE STATISTICS

We will tabulate baseline characteristics of the two trial arms for potential imbalance in variables. Continuous variables will be summarized by typical parameters such as mean, standard deviation and range and compared using two-sample T test (if the normality assumption holds) or Wilcoxon rank-sum test (if the normality assumption does not hold).

Normality of distribution will be determined using the Kolmogorov-Smirnov goodness-of-fit test. Categorical data will be summarized by frequency and percentage and analyzed using the Chi-square or Fishers exact test, as appropriate.

The use of prior and concomitant medications will be summarized. The use and doses of IV and oral loop diuretics in furosemide equivalents will be summarized by treatment group. Other concomitant medications will be coded using WHO Drug and summarized by treatment group according to Anatomic Therapeutic Classification and preferred term.

10.4.3 ANALYSIS OF THE PRIMARY EFFICACY ENDPOINT(S)

The total number of B-lines at the conclusion of ED AHF management

We will examine the distribution of B-lines measurements for the groups with and without events separately. Both absolute number and relative change will be evaluated. Receiver Operating Characteristic (ROC) curves will be plotted together with area under the curve (AUC) calculated to understand the prediction performance of the B-line measurements. Sensitivity, specificity, positive and negative predictive values will be computed at a number of thresholds of B-line measurements to understand the trade-off between false positive and false negative. Confidence intervals of statistical measures will be constructed using the bootstrap method.⁹¹ Although 15 B-lines have been previously identified as a valid threshold, an alternative number may be more useful in the ED setting.

Potential covariates will also be considered in a logistic regression setting to improve precision, which includes baseline co-morbidities, baseline medications (in particular guideline recommended therapies) in-hospital medications, baseline renal function, serum sodium, natriuretic peptide levels, troponin levels, renal function, baseline blood pressure, and discharge medications. Variables such as physical exam, other vital signs, and hemoconcentration may also be included. These covariates are known markers of risk and are standard of care assessments for the vast majority of AHF admissions. Covariates with univariately significant association with the outcome will be included together with the treatment indicator in a logistic regression model. Due to limited sample size, we will limit the number of covariates (including treatment indicator) such that there is 10 events per covariate.

ANALYSIS OF THE SECONDARY ENDPOINTS

1. Dyspnea will also be assessed using a 5-point and 7-point Likert scale.

Dyspnea will be assessed at the baseline and 6 hours later (or closest time point prior to ER discharge using two instruments. Dyspnea will also be assessed at any time between D2 and D/C. A 7-point Likert scale to determine change from baseline: 1) markedly worse, 2) moderately worse, 3) minimally worse, 4) no change, 5) minimally improved, 6) moderately improved, 7) markedly improved. However, patients may not recall accurately how they felt at baseline or be uncertain about when baseline was supposed to be. Also, patients with severe symptoms who don't respond and patients whose symptoms were initially mild and have little room to improve may end up with similar change scores. Accordingly, symptoms were also assessed using an absolute scale. Change in dyspnoea can be calculated by subtracting scores. A 5-point Likert scale was used to document patients' current status: 1) not short of breath at all, 2) mildly short of breath, 3) moderately short of breath, 4) severely short of breath, 5) very severely short of breath.

Patients were placed at 45 degrees for all questioning. If patients were recently up and walking, at least 2 minutes of equilibration is required.

Change scores between responses at baseline and 6 hours on the 5-point Likert scale items and the VAS were calculated by subtracting the baseline value from the 6-hour value. These change scores were categorized as improvement, worsening and no change. Fisher's exact tests were used to compare the 3 groups by either definition on changes in the 5-point Likert scale

2. The comparison of binary endpoints (B-lines ≤ 15) will be performed using Chi-square or Fishers exact test, as appropriate.

As 15 B-lines have been previously shown to be associated with worse outcomes, a difference of 15 B lines will be considered significant for this study.

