- That I will be responsible for maintaining each patient's consent form in the study file and provide each patient with a signed copy of the consent form.

Investigator Name and Title:

Institution Address:

Signature: _____

Date: _____

PROTOCOL SUMMARY

Title: *"Nitroglycerin vs. Furosemide using Lung Ultrasound Pilot Trial" (N-FURIOUS)*

[figure not shown]
Précis: Of the one million admissions for AHF in the US, approximately 80% are initially managed in the ED. Outcomes from AHF are poor: nearly 25% are dead or re-hospitalized within 30 days of discharge. The evidence base to treat AHF is limited. In fact, there are no pharmacologic therapies with Class I, Level A guideline recommendations. The acute

treatment of patients today is largely the same as 40 years ago. This proposal aims to build the evidence base for ED AHF care.

Using a two-site, randomized controlled design, this pilot study will test whether a nitrate intense strategy more effectively reduces congestion, defined by LUS B-lines, better than a diuretic intense strategy.

Objectives:	1: To determine whether a nitrate intense strategy safely reduces congestion, defined by LUS B-lines, better than a diuretic intense strategy. 2: To demonstrate feasibility of recruitment and compliance with study protocol to inform future study design and enrollment projections, an external site will also test our study protocol.
Endpoint	A comparison of total B-lines at the conclusion of ED AHF management or maximum of 6 hours after enrollment, whichever comes first.
Population:	Emergency department (ED) AHF patients. All patients who meet inclusion and no exclusion criteria will be enrolled during their ED visit within 3 hours of presentation.
Phase:	2
Number of Sites enrolling participants:	Two sites (3 total hospitals). Projected sample size, n=70.
Description of Study Agent:	Nitrate intense vs. Diuretic intense AHF treatment strategy
Study Duration:	2 years. There will be three months of start up, and one month of study conclusion work. Enrollment will occur over 20 months, which equals 3.5 patients month. As there will be staggered start up to determine replication, approximately 1-2 patients/month.
Participant Duration:	30 days post discharge

SCHEMATIC OF STUDY DESIGN

*whichever comes first

**Presentation is defined as first time recorded when placed in a room to be treated. This allows patients to still be enrolled despite a long waiting room time

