4.2.1 PRIMARY ENDPOINT

The total number of B-lines at the conclusion of ED AHF management

Main Secondary Endpoints:

Dyspnea will also be assessed using a 5-point and 7-point Likert scale.

B-lines ≤ 15 at the conclusion of ED AHF management

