7.3.4 SCHEDULE OF EVENTS TABLE

Schedule of Events	Screening	Day 1 T00	Day 1 T02-04	Day 1 T06	Day 2-6 T24-D6	30 day follow up
Informed consent (I/E)	X					
Medical History	X					
Medication history	X					
Clinical Assessment#		X	X	X	X	
Body Weight, height, Vital Signs	ED SOC	VS only	VS only	VS only	BW/VS only	
5-point and 7-point Likert scale		X		X	X	
Labs: Electrolytes, hematology, NP, eGFR, Troponin	ED SOC					
12-lead ECG	ED SOC					
CXR	ED SOC					
LUS B-lines 8 zone	X (LUS T00)		X	X	X ^{^^}	
Nitrate vs. Diuretic intense management		X	X	X		
Lab draw: eGFR, Hgb/Hct [^]		X				
eCRF/data collection/verification		X				X
Assessment of AE/SAE's						X
Phone follow-up Vital Status						X

Subject payment		X				X
-----------------	--	---	--	--	--	---

SOC = standard of care, ED = Emergency Department, I/E = inclusion, exclusion, CV = cardiovascular, LUS = lung ultrasound, BW = body weight, NP = natriuretic peptide ^if collected as part of standard of care, will use that result. The last collected result will be used if not drawn on or close to discharge ^^ LUS to be performed up to 48 hours after hospitalization. If an obs unit patient, prior to discharge.

Further detail regarding timing of assessments: [NOTE: given clinical circumstances (i.e. left the ER for a test, discussion with consultant, etc) – the SITE PI has final discretion to continue to image a patient before or after the allotted window. This time MUST be recorded in the eCRF]

- T00: initial LUS scan (in ED for screening and eligibility)
- T02: 2-4 hours after initial treatment (in ED) (+/- 30 minutes)
- T06: 2-4 hours after T02 or pre-ED discharge, whichever comes first (+/- 60 minutes)
- T48: up to 48 hours after initial scan (Day 3) (+/- 12 hours)

** For vital signs during hospitalization. The nearest vital signs to the LUS exam will be captured.

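### Section 10.4.3, the primary efficacy analysis, describes a prognostic ROC and logistic plan and names no between-arm test or estimate of total B-lines

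*Combined protocol and SAP*

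**What the plan says.** Section 4.2.1 gives the primary endpoint as "The total number of B-lines at the conclusion of ED AHF management". The Protocol Summary frames it as "A comparison of total B-lines at the conclusion of ED AHF management or maximum of 6 hours after enrollment, whichever comes first". Hypothesis 1a in Section 10.2 is that "Nitrate intense treated patients will have less congestion, defined by LUS B-lines, than diuretic intense patients at 6 hours after start of treatment". Section 10.5 powers the trial for a difference of 7 B-lines between arms: effect size 0.7, 35 per arm, two-sided 0.05, 82% power.

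Section 10.4.3 repeats the endpoint and then begins: "We will examine the distribution of B-lines measurements for the groups with and without events separately". It goes on to ROC curves and AUC, sensitivity, specificity and predictive values at a range of B-line cut-offs, and bootstrap intervals. Absolute and relative change are both mentioned, with no choice between them and no reference to arms.

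Treatment appears once: "Covariates with univariately significant association with the outcome will be included together with the treatment indicator in a logistic regression model". Candidate covariates include in-hospital medications, hemoconcentration and "renal function, baseline blood pressure, and discharge medications". On model size, "we will limit the number of covariates (including treatment indicator) such that there is 10 events per covariate".

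**The concern.** Section 10.4.3 answers a different question from the one the trial asks. It groups patients by undefined events rather than by arm, and it uses B-lines as a predictor rather than as the outcome. The one model that contains treatment is logistic, so its outcome must be binary; it cannot estimate a difference in a count.

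The primary hypothesis therefore has no pre-specified test or effect estimate. Treatment is unblinded (Section 10.6.1), and Section 10.4.1 makes no adjustment for multiple comparisons. The choice among raw count, relative change, a rank test and an adjusted model would be open once data are in hand. The pilot is meant to supply what a definitive trial needs (Section 3). The B-line difference with its interval is its key efficacy output, and the plan does not say how it will be obtained.

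Two lesser faults sit in the same text. Adjusting for variables measured after randomisation can bias the treatment effect, because treatment may change them. Selecting covariates by univariate significance makes the model depend on the data.

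**Working it through.** **1. Is the comparison specified elsewhere?** Methods assigned in Section 10:

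| Variable | Method | Section |
|---|---|---|
| Baseline variables | t-test or Wilcoxon; chi-square or Fisher | 10.4.2 |
| Total B-lines (primary) | no between-arm method | 10.4.3 |
| Dyspnea change categories | Fisher | 10.4.3, secondary |
| B-lines ≤15 | chi-square or Fisher | 10.4.3, secondary |
| DAOOH | t-test or Wilcoxon; proportional odds | 10.4.4 |
| B-line association with 30-day outcomes | none | 10.4.4 |
| Safety variables | t-test or Wilcoxon; chi-square or Fisher | 10.4.5 |

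Section 10.4.1 sets only the significance level, and Section 10.3 only the analysis sets. The ROC and event text fits the 30-day association items, which have no method of their own. That it is misplaced is an inference.

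**2. Reproduce the stated power.** Inputs from Section 10.5: difference 7, effect size 0.7, n=35 per arm, two-sided 0.05.
- Implied SD = 7/0.7 = 10 lines (not stated in the plan).
- Noncentrality = 0.7 × √(35/2) = 2.93, df = 68. Power = **82.3%**, matching the stated 82%.
- 95% CI half-width = t(0.975, 68) × 10 × √(2/35) = 1.995 × 2.39 = **4.8 lines**.

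The power belongs to a two-sample comparison of means.

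**3. Could the logistic model stand in?** Suppose its outcome is B-lines ≤15. Take SD 10, a 7-line shift, normal data and assumed control means of 15 to 30. The arm proportions are Φ((15−m)/10) and Φ((22−m)/10):

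| Control mean m | Control | Shifted arm | Power, 35 per arm |
|---|---|---|---|
| 15 | 0.500 | 0.758 | 61% |
| 18.5 | 0.363 | 0.637 | 63% |
| 25 | 0.159 | 0.382 | 56% |
| 30 | 0.067 | 0.212 | 42% |

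This gives 42% to 63%, not 82%, and B-lines ≤15 is a secondary endpoint with its own test.

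**4. What does the 10-events rule allow?** If events are 30-day deaths or rehospitalisations at 25% (the Summary says nearly 25%, Section 2.1 over 25%), 70 × 0.25 = 17.5 events. That allows one term, treatment alone. A second term needs 20 events, or 20/70 = 28.6%. If the outcome is B-lines ≤15, the expected count is 35 × (0.363 + 0.637) = 35 at m = 18.5 (three terms), but 35 × (0.067 + 0.212) = 9.8 at m = 30 (none).

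**5. Candidate replacements at N=70.**
- Two-sample t-test: 82.3%.
- Wilcoxon on normal data: about 81% (80.5% using relative efficiency 3/π; 81.2% simulated).
- ANCOVA on baseline B-lines and three hospitals: effect size 0.7/√(1−ρ²), df = 70 − 5 = 65, where ρ is the baseline-to-endpoint correlation. The documents do not give ρ, so a range is shown:

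| ρ | 0 | 0.2 | 0.3 | 0.5 | 0.7 |
|---|---|---|---|---|---|
| Power | 82.2% | 83.8% | 85.6% | 91.5% | 98.1% |

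In a simulation with allocation balanced within three hospitals and ρ = 0 (40,000 replicates), ANCOVA gave 81.7% and the t-test 82.4%. Adjustment therefore costs under 1 point at worst and gains about 1 to 16 points for ρ from 0.2 to 0.7. Entry at more than 15 B-lines may hold ρ low.

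**6. Time point.** The Summary caps the assessment at 6 hours after enrollment, Section 4.2.1 uses the end of ED management, and Section 10.2 uses 6 hours after start of treatment. In Section 7.3.4 the T06 scan follows T02 by 2–4 hours, and T02 follows first treatment by 2–4 hours. That is nominally 4 to 8 hours before the windows are applied, or earlier at ED discharge. Section 6.1.1 also offers 6 hours after start of treatment as one of three options for the second re-assessment.

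**The case against.** The strongest reply is that the intended analysis is plain. Section 10.5 reproduces only as a two-sided comparison of two means, Section 10.3 fixes the population, and the t-test/Wilcoxon convention appears for baseline, DAOOH and safety. Those two tests have nearly the same power, so choosing between them matters little. Core Lab readers are blinded, and their readings are withheld from investigators until database lock (Section 17.3). Feasibility is an equal objective of a study the plan calls exploratory.

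Part of this stands. The power statement shows what was probably meant, and blinded reading protects the measurement. But a power statement does not choose between absolute and relative change, or between adjusted and unadjusted analysis, and blinded reading does not constrain a later choice of model. A pilot that states a directional hypothesis, a significance level and 82% power still needs the matching test.

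It is also fair that ANCOVA is a preference rather than a necessity, that the gains rest on an assumed correlation and normal data, and that the event count depends on what the undefined events are. Treatment continues until B-lines reach 15 or fewer, or 6 hours (Section 4.1), so endpoint values may cluster near 15. That is a reason for a pre-specified sensitivity analysis.

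**Conclusion.** The point holds and must be fixed. It is an error in the stated analysis, not a missing detail: carried out as written, Section 10.4.3 neither tests Hypothesis 1a nor delivers the analysis behind the 82% power. This conclusion rests on the text alone. The sample size needs no change. The ±4.8-line interval assumes the implied SD of 10; the ANCOVA and dichotomised power figures rest on the assumed correlations, control means and normality shown above. The covariate faults, the differing time points and the 15-line sentence are secondary, but belong in the same revision.

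**What to change.** Replace the primary text of Section 10.4.3 with wording such as: *Total B-lines at the primary time point will be compared between arms in the FAS by linear regression with treatment, T00 total B-lines and site, reporting the adjusted mean difference, 95% CI and two-sided p-value. A rank-based or bootstrap analysis is the sensitivity analysis for skew.* An unadjusted t-test or Wilcoxon test, named in advance, would cure the core defect.

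In the same revision:
- Define one primary time point and word it identically in the Summary, 4.2.1, 10.2 and 10.4.3. T06 is a natural candidate once Sections 6.1.1 and 7.3.4 are reconciled with it.
- Remove post-randomisation covariates and univariate selection from any model that estimates the treatment effect.
- Move the ROC, threshold and event text to Section 10.4.4 and define the events there.
- Reword the sentence under the secondary endpoints that treats a 15-line difference as significant, so that it is not a second criterion beside the 7 lines in 10.5.
- State whether the site or Core Lab count is primary, and reconcile the per-sector maximum (20 in Section 17.1, 10 in 17.3, so an eight-sector total of up to 160 or 80). This is a separate issue, but the new analysis needs a defined outcome.

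The cost is text only. T00 and T06 B-lines and site are already scheduled or recorded, although Section 6.1.1 allows some re-assessments to be missed. Because the endpoint and hypothesis sections also change, the revision is a protocol amendment needing ethics approval under Section 12, which allows expedited review of minor changes.
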